### 1.3 Drug Class

DS107 capsules contain the active pharmaceutical ingredient (API) DGLA a long-chain polyunsaturated fatty acid endogenously present in the body.

Figure 1: Structure of DGLA

### 1.4 Preclinical Pharmacology

Numerous preclinical studies have been performed to determine the mechanisms of action of DS107 in inflammatory skin diseases including AD. The results of the studies have highlighted a multi-modal

mechanism of action in which DS107 exerts its therapeutic effect, including direct anti-bacterial mechanisms as well as direct and indirect anti-inflammatory mechanisms.

The effect of DS107 on the release of proinflammatory cytokines from human monocytes has been studied and shows that DS107 significantly reduces the secretion of IL-1 $\beta$  and IL-8 from triggered monocytes. Both IL-1 $\beta$  and IL-8 play an important role in the pathogenesis of AD. Inhibition of these pro-inflammatory pathways with DS107 capsules may provide significant improvements in the clinical manifestations of AD. It has been shown that metabolism of DGLA via COX-1 and COX-2 pathways results in the production of potent anti-inflammatory eicosanoids such as prostaglandins (specifically PGD1) and thromboxanes (Kawashima *et al.* 2008; Amagai *et al.* 2015). Additionally, lipoxygenation of DGLA results in the production of monohydroxy fatty acid 15-hydroxyeicosatrienoic acid (15-HETrE) which has shown potent anti-inflammatory properties (Iverson *et al.* 1992).

In addition to anti-inflammatory mechanisms, DS107 significantly inhibits the growth of *Staphylococcus aureus* and *Propionibacterium acnes* and also has direct bactericidal activity against both (Desbois & Lawlor 2013).

DGLA has been reported to suppress acute and chronic inflammation in whole preclinical mouse studies. Oral administration of up to 600 mg/kg DGLA has shown dose dependent improvements in severity of skin lesions in animal models of AD. DGLA treatment is correlated with decreased plasma total IgE concentrations which may contribute to resolving the AD lesions (Kawashima *et al.* 2008).

In the same study DGLA also significantly decreases the number of scratch events and duration of scratching in animal models of AD (Kawashima *et al.* 2008; Amagai *et al.* 2015). The improvement in clinical scores and pruritus has been associated with the generation of PGD1 via DGLA metabolism (Amagai *et al.* 2015).

## 1.5 Toxicology

### Oral Toxicology

A 13-week oral study in rats using DGLA did not show any significant treatment-related adverse events and so the No Observed Adverse Event Limit (NOAEL) was set at 2000 mg/kg per day. Read-across from linoleic acid would suggest that repeated exposure to DS107 capsules at levels found in this product is unlikely to cause adverse effects (Kawashima *et al.* 2009).

DS107 was very well tolerated in rats given up to 2,000 mg/kg/day for up to 26 weeks. Safety margins at the NOAEL in this study (2,000 mg/kg/day) were very large (i.e., 18- to 30-fold and 11- to 24-fold that seen in human subjects given 4g/day DS107 when based on unesterified DGLA for AUC and Cmax, respectively). In dogs, a pattern of dose-related, intermittent/sporadic, limb withdrawal and/or limited limb usage was seen at repeated doses >150 mg/kg/day in the 39-week study. This effect was completely reversible upon cessation of dosing. There was no correlative finding, including histopathology at the affected joints that could explain this effect. The NOAEL for this effect was 50 mg/kg/day, which corresponded to a safety margin of 1.1- to 1.6-fold and 3.1- to 3.7-fold greater than that seen in human subjects given 4g/day DS107 for AUC and Cmax, respectively. Lack of similar DS107 related effects on mobility in rats (doses up to 2g/kg/day for 26 weeks) and humans (doses up to 4g/day for 8 weeks) suggests the effect in dogs is species specific.

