## 1.6 Previous Clinical Studies with DS107

DS107 is being studied in oral (capsule) and topical (cream) formulation. Topical DS107 has been administered to 524 subjects during the course of one Phase 1 trial (DS107E-01) and five Phase 2 trials (DS107E-02, DS107E-03, DS107E-04, DS107E-05, DS107E-06). In addition, three well-controlled clinical studies have been conducted to assess the safety and efficacy of DS107 capsules. To date, DS107 capsules has been administered to 304 healthy volunteers/patients during the course of one Phase 1 trial (DS107G-01) and two Phase 2 trials (DS107G-02 & DS107G-03) for AD. Up to 4g DS107 capsules has been clinically tested and is well tolerated in healthy volunteers and patients with moderate to severe AD. Below are a list of the completed studies which utilise DS107 capsules.

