### **DS107 Capsules Phase 1 Study (DS107G-01)**

This study was a randomised, double-blind, placebo-controlled, single-ascending dose and multiple dose Phase 1 study to assess the safety, pharmacokinetics and effect of food on orally administered DS107 in 48 healthy volunteers. In the single dose part of the study healthy volunteers were randomised to 4 cohorts and administered either 500mg, 1g, 2g or 4g DS107 capsules. In the multiple dose of the study healthy volunteers were randomised to 2 cohorts and administered either 2g or 4g DS107 capsules once daily for 28 days.

Under fasted conditions, both free and total DGLA increased in a linear manner following oral administration. Although not evaluated statistically, administration of a single 1g dose of DS107 capsules under fasted conditions resulted in an approximately 50% higher rate.

There were no deaths, Serious Adverse Events (SAEs), discontinuations due to AEs, considered to be not recovered/resolved, or AEs considered to be definitely related to study drug in this study. The most common AEs were gastrointestinal in nature which were of relatively short duration and resolved without intervention.

Overall, DS107 capsules administered to 48 healthy volunteers as a single 500mg, 1g, 2g, or 4g dose under fasted conditions; as a single 1g dose under fed conditions; and as multiple 2g and 4g doses taken once daily for 28 consecutive days was well tolerated.

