## **2 RISK BENEFIT ASSESSMENT**

To date, DS107 capsules has been administered to 304 healthy volunteers/patients during the course of one Phase 1 trial (DS107G-01) and two Phase 2 trials (DS107G-02 & DS107G-03) for AD. Up to 4g DS107 capsules has been clinically tested and is well tolerated in healthy volunteers and patients with moderate to severe AD. 2g DS107 capsules was well tolerated and safe in 164 patients with moderate to severe AD.

The effect of DS107 capsules on the signs and symptoms of AD, efficacy endpoints and pharmacodynamic biomarkers was consistently superior to placebo in Phase 2 clinical studies in patients with moderate to severe AD, with a similar pattern in both Investigator scores and patient scores.

Based on the endogenous nature of the active pharmaceutical ingredient, exposure margins from non-clinical toxicology studies, a favourable clinical safety profile observed in three clinical studies and the observed therapeutic efficacy of DS107 capsules in a disease with a persistent unmet need for additional effective and well tolerated therapies, it can be concluded that there is a positive risk-benefit ratio for the continued investigation of DS107 capsules as a treatment for moderate to severe AD.

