### 9.2.2 Physical Examination

A physical examination will be performed by the Investigator as per the Study Flow Chart (Appendix 1) in accordance with local practices. This examination will be symptom-directed, i.e., a standard panel of body systems will not be assessed unless indicated by patient. For example should the patient report to the Investigator the presence of 'rash' then the skin would be evaluated. It is not required that additional body systems are assessed unless clinically warranted. Any clinically significant abnormal results should be recorded in the CRF. Changes in findings of the physical examination compared with the baseline examination should be recorded as an AE.

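### The human exposure used in Section 1.5 to call the dog limb effect species specific (4 g/day for 8 weeks) matches no listed study, and this longer trial has no prompted check on limb use

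*Protocol*

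**What the plan says.** Protocol Section 1.5 (Oral Toxicology) reports that in dogs "limb withdrawal and/or limited limb usage was seen at repeated doses >150 mg/kg/day in the 39-week study". It adds that the effect was dose-related and came and went, that it reversed fully when dosing stopped, and that no finding, including joint histopathology, explained it. The dose without the effect was 50 mg/kg/day, with a "safety margin of 1.1- to 1.6-fold and 3.1- to 3.7-fold greater than that seen in human subjects given 4g/day DS107", for AUC and Cmax respectively. The section then gives two grounds for regarding the effect as peculiar to dogs: "Lack of similar DS107 related effects on mobility in rats (doses up to 2g/kg/day for 26 weeks") and its absence in "humans (doses up to 4g/day for 8 weeks) suggests the effect in dogs is species specific".

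Section 1.6 says that capsules have been given in "one Phase 1 trial (DS107G-01) and two Phase 2 trials (DS107G-02 & DS107G-03) for AD". In the Phase 1 study, the repeat-dose cohorts were "administered either 2g or 4g DS107 capsules once daily for 28 days". Table 1 and the Phase 2 summaries give 2 g (DS107G-02) and 1 g or 2 g (DS107G-03), each for 8 weeks. Sections 1.6 and 2 both state: "Up to 4g DS107 capsules has been clinically tested and is well tolerated in healthy volunteers and patients with moderate to severe AD".

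In this trial the physical examination is symptom-directed. Section 9.2.2 says that "a standard panel of body systems will not be assessed unless indicated by patient". Adverse events are assessed at each post-baseline visit. SAP Section 7.5 tabulates them by system organ class and preferred term.

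**The concern.** A safety signal from animals is discounted partly on human experience that the protocol's own study list does not show. The dog finding has a much narrower AUC margin (1.1 to 1.6 at the no-effect dose, against human exposure at 4 g/day) than the rat study (18 to 30), so the human evidence carries real weight in the argument.

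The effect was seen in a 39-week study, so duration may matter, and this trial gives capsules for longer than any listed study did. An intermittent, reversible problem with limb use is the kind of event a patient with eczema may not volunteer. If nobody asks, a low count is hard to interpret.

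**Working it through.** **1. Look for the stated exposure.** The claim is 4 g/day for 8 weeks: 4 × 56 = 224 g in total. The capsule exposures in Table 1 and the Section 1.6 summaries, with this trial added, are:

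| Study | Population | Daily dose | Days | Total |
|---|---|---|---|---|
| DS107G-01 | healthy volunteers | 2 g | 28 | 56 g |
| DS107G-01 | healthy volunteers | 4 g | 28 | 112 g |
| DS107G-02 | patients | 2 g | 56 | 112 g |
| DS107G-03 | patients | 1 g | 56 | 56 g |
| DS107G-03 | patients | 2 g | 56 | 112 g |
| This trial | patients | 2 g | 112 | 224 g |

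DS107G-01 also gave single doses of up to 4 g. No earlier row has both 4 g and 56 days, so the figure cannot be reproduced. Section 3 likewise attributes the safety data up to 4 g to the Phase 1 study.

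**2. Try the other reading.** As two separate maxima, 4 g (Phase 1) and 8 weeks (Phase 2) both exist, but in different people. The rat phrase beside it has the same form and describes one study in which the top dose and the duration went together, so separate maxima is a strained reading.

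**3. How much 4 g repeat-dose evidence is there?** The number given 4 g for 28 days is not stated. An inference from stated figures:
- DS107G-02 active arm: 29 moderate + 22 severe or very severe = 51.
- DS107G-03 2 g arm: 164 patients on 2 g (Section 2) − 51 = 113.
- DS107G-03 1 g plus placebo: 321 − 113 = 208. The reported adverse-event percentages (33.7% and 32.7%) fit 1 g arms of 95, 98, 101 or 104.
- DS107G-01 on active drug: 304 − 164 − (95 to 104) = 45 to 36.
- Over six cohorts, assumed equal: 6 to 7.5, so about 6 to 8 people.

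With zero events in n people, the exact one-sided 95% upper limit for the event rate is 1 − 0.05^(1/n):
- n = 6: 39%
- n = 8: 31%
- n = 12 (if the cohort was larger than inferred): 22%
- n = 164 (2 g, if all were followed for 8 weeks with no event): 1.8%

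The 2 g data are thus far more informative than the 4 g data, but they stop at 8 weeks.

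**4. The margin at this trial's dose.** If exposure is proportional to dose, halving 4 g doubles the margins at the dog no-effect dose: AUC 2 × (1.1 to 1.6) = 2.2 to 3.2; Cmax 2 × (3.1 to 3.7) = 6.2 to 7.4. Proportionality is an assumption. Section 1.6 reports a linear rise under fasted conditions, and DGLA is endogenous. If a natural background level is included in the measured exposure, the margins would lie between the 4 g and the doubled values.

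**5. What this trial would pick up.** The flow chart, Section 9.2 and SAP Sections 7.5 and 8 contain no question, examination item or event grouping for limbs, joints, gait or mobility. On-treatment site visits after Week 4 are four weeks apart.

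**The case against.** The strongest reply is that this is an error in background text with little consequence. Much of that stands:

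- The inference has a second leg in the rat data, and the text says only that the evidence suggests species specificity. Reversibility and the lack of a tissue correlate are reported openly.
- The 1.1- to 1.6-fold figure is the AUC margin at the dose that produced no effect, measured against 4 g/day. It is not the margin to the effect, which appeared above 150 mg/kg/day, more than three times the no-effect dose. It is also not the margin at this trial's 2 g.
- The Section 2 sentence on 4 g can be read as a range across both groups, and the next sentence gives 2 g in 164 patients. It is loose rather than plainly false.
- A volunteered limb complaint would be recorded, would prompt a directed examination and would appear in the preferred-term tables. CPK is measured at laboratory visits. Nothing in the documents shows that general enquiry would miss such events, and nothing commits the trial to a targeted check.

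A reader might go further and infer that the positive risk-benefit conclusion rests on human exposure that does not exist. The documents do not support that. Section 2 cites the endogenous ingredient, non-clinical margins, the safety profile of three clinical studies and observed efficacy. The toxicology conclusion in Section 1.5 relies on exposure at the no-effect doses in the 26-week rat and 39-week dog studies. Neither cites 4 g for 8 weeks.

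An unlisted study is conceivable, since this trial is numbered DS107G-05 and the list ends at DS107G-03. But Sections 1.6, 2 and 3 all count three clinical studies. If another exists, it belongs in that list.

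What the reply does not answer is the mismatch itself, or the absence of any prompted check in a trial of twice the longest listed duration.

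**Conclusion.** The point holds in a limited form. One of the two grounds given for species specificity cites a human exposure that no listed study provides: 4 g/day was given for at most 4 weeks rather than 8, in healthy volunteers, and no listed patient study exceeded 2 g. The argument is weakened, not overturned, and the overall risk-benefit conclusion does not depend on this figure alone. Nothing here shows that the effect occurs in people.

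The practical weight comes from duration: 16 weeks against 8, and 224 g in total against at most 112 g, with no prompted enquiry. The mismatch rests only on the protocol's own text. The cohort size of about 6 to 8 and the doubled margins at 2 g rest on the assumptions stated above, and the conclusion does not need either. This should be corrected; it does not undermine the efficacy analysis.

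**What to change.** Reconcile the dose and duration statements in Section 1.5, the opening of Section 1.6 and Section 2 with Table 1 and the study summaries. Then restate the species-specificity argument on documented exposures, giving the number of people at each dose and duration. If a further study supports the present wording, list it.

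Add one prompted question on limb use and mobility to the adverse-event assessment at the existing visits, worded identically in both arms. Add one grouped row to the SAP adverse-event tables, by arm, for limb, joint and gait events, with the preferred terms fixed before unblinding. State in the protocol how the safety assessments address the dog finding.

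The cost is a text correction, one question and one table row. The downside is slightly more adverse-event reports in both blinded arms. No change to dose, schedule or stopping rules is proposed.

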### Topical Toxicology

Local tolerance has been assessed in several non-clinical studies, the most relevant of which is the GLP-compliant toxicity study, conducted by Charles River Laboratories (CRL Study-521831, 2012), in which DS107 cream was applied topically daily for 13 weeks to minipigs. Reaction to treatment was seen at the administration sites as very slight to well-defined erythema with red spots on or outside the edges of sites and dry flaky skin in some cases. Reactions were mild to moderate and 91-day treatments were completed for most animals. All findings were reversible. In this study there were no histopathology findings at main study kill (Day 92) attributed to treatment. Microscopic findings at the

different treatment sites were considered to have arisen spontaneously and/or to have been associated with the administration procedure. Other microscopic findings observed were considered incidental, of the nature commonly observed in this strain and age of minipig. They were of similar incidence and/or severity in control and treated animals and were therefore considered unrelated to administration of DS107 Cream. Toxicokinetic analysis of plasma samples taken from the minipigs over the 13-week treatment period did not show any significant systemic exposure of DS107 following topical administration.

### Mutagenicity

Previously, DGLA exhibited no mutagenicity in an Ames test regardless of the presence or absence of S9 mix (Kawashima *et al.* 2009). A recent DS Biopharma sponsored Ames test showed no substantial increases in revertant colony numbers with any of the tester strains following exposure to DS107, at any dose level, in the presence or absence of S9 mix. Therefore, DS107 was considered to be negative for the induction of mutagenicity in this *in vitro* assay when tested in accordance with regulatory guidelines. Furthermore, in a mouse lymphoma assay sponsored by the company, DS107 was not associated with genotoxicity in the presence or absence of metabolic activation.

### Conclusion

No undue toxicological hazard or risk for patients treated with DS107 capsules has been identified in a battery of non-clinical toxicology studies. 26-week rat and 39-week dog chronic toxicity studies with greater systemic exposure at the determined NOAEL than human subjects receiving doses of oral DS107 capsules of up to 4g daily are considered adequate to support further clinical trials of greater than 6 months duration (per ICH M3 (R2)) for subjects given daily oral DS107 doses of up to 4g daily.

## 1.6 Previous Clinical Studies with DS107

DS107 is being studied in oral (capsule) and topical (cream) formulation. Topical DS107 has been administered to 524 subjects during the course of one Phase 1 trial (DS107E-01) and five Phase 2 trials (DS107E-02, DS107E-03, DS107E-04, DS107E-05, DS107E-06). In addition, three well-controlled clinical studies have been conducted to assess the safety and efficacy of DS107 capsules. To date, DS107 capsules has been administered to 304 healthy volunteers/patients during the course of one Phase 1 trial (DS107G-01) and two Phase 2 trials (DS107G-02 & DS107G-03) for AD. Up to 4g DS107 capsules has been clinically tested and is well tolerated in healthy volunteers and patients with moderate to severe AD. Below are a list of the completed studies which utilise DS107 capsules.

**Table 1: Summary of DS107 Capsules Use in Human Healthy Volunteers/Patients**

DS107G-01					
A Randomised, Double-Blind, Placebo-Controlled, Single-Ascending Dose and Multiple Dose Phase 1 Study to Assess the Safety, Pharmacokinetics and Effect of Food on Orally Administered DS107 in Healthy Subjects.					
Phase	Duration	Indication	IMP Concentration	# Healthy Volunteers	Status
1 (safety)	Single Dose and Multiple Dose (28 days)	Healthy Volunteers	500mg 1g 2g 4g	48	Completed
DS107G-02					
A Randomised, Double-blind, Placebo-Controlled, Phase 2 Study to Assess the Efficacy and Safety of Orally Administered DS107 to Patients with Moderate to Severe AD					

Phase	Duration	Indication	IMP Concentration.	# Patients	Status
2a (safety & efficacy)	8 Weeks	Moderate to Severe AD	2g	102	Completed
DS107G-03					
A Randomised, Double-blind, Placebo-controlled, Phase 2b Study to Assess the Efficacy and Safety of Orally Administered DS107 in Patients with Moderate to Severe Atopic Dermatitis					
Phase	Duration	Indication	IMP Concentration.	# Patients	Status
2b (safety & efficacy)	8 Weeks	Moderate to Severe AD	1g 2g	321	Completed

### **DS107 Capsules Phase 1 Study (DS107G-01)**

This study was a randomised, double-blind, placebo-controlled, single-ascending dose and multiple dose Phase 1 study to assess the safety, pharmacokinetics and effect of food on orally administered DS107 in 48 healthy volunteers. In the single dose part of the study healthy volunteers were randomised to 4 cohorts and administered either 500mg, 1g, 2g or 4g DS107 capsules. In the multiple dose of the study healthy volunteers were randomised to 2 cohorts and administered either 2g or 4g DS107 capsules once daily for 28 days.

Under fasted conditions, both free and total DGLA increased in a linear manner following oral administration. Although not evaluated statistically, administration of a single 1g dose of DS107 capsules under fasted conditions resulted in an approximately 50% higher rate.

There were no deaths, Serious Adverse Events (SAEs), discontinuations due to AEs, considered to be not recovered/resolved, or AEs considered to be definitely related to study drug in this study. The most common AEs were gastrointestinal in nature which were of relatively short duration and resolved without intervention.

Overall, DS107 capsules administered to 48 healthy volunteers as a single 500mg, 1g, 2g, or 4g dose under fasted conditions; as a single 1g dose under fed conditions; and as multiple 2g and 4g doses taken once daily for 28 consecutive days was well tolerated.

### **DS107 Capsules Phase 2a Study (DS107G-02)**

This 8 week study was a randomized, placebo-controlled, double-blind, multi-centre Phase 2a trial to investigate the efficacy, safety, tolerability and bioavailability of 2g DS107 administered orally once daily versus 2g placebo administered orally once daily in adult patients with moderate to severe AD. The primary efficacy endpoint was defined as the proportion of patients achieving an Investigator Global Assessment (IGA) of 0 (clear) or 1 (almost clear) and a decrease of at least two points in IGA at Week 8. Secondary efficacy variables included IGA measurements, pruritus (obtained from the SCORAD VAS), EASI, BSA, POEM, DLQI and SCORAD.

There was a trend toward a statistically significant higher number of patients who achieved an IGA score of 0 or 1 and a 2 point drop in the DS107 capsules group at Week 8 in comparison to placebo: 11 (21.6%) responders in the DS107 capsules group, and 6 (11.8%) in the placebo group (p-value: 0.057). A similar trend was also observed in the number of patients achieving a decrease of at least 2 points in the IGA score at Week 8 with 14 (27.5%) in the DS107 capsules group and 8 (15.7%) in the placebo group (p-value: 0.065).

Further analysis was performed on the severity groups (moderate and severe/very severe at baseline) comparing the DS107 capsules group to the placebo group in terms of responders, using the Cochran-Mantel-Haenszel (CMH) test stratified for site. The proportion of responders was always greater in the DS107 capsules group compared to the placebo group in both the moderate and the severe/very severe populations.

The proportion of moderate patients achieving an IGA of 0 (clear) or 1 (almost clear) and a decrease in 2 point in IGA score was significantly greater in the DS107 capsules group (8/29 patients, 28%) compared to placebo group (6/38 patients, 16%) in patients with moderate AD at baseline ( $p = 0.036$ ). Similar efficacy trends were observed in the severe/very severe population where 3 out of 22 patients (13%) treated with DS107 capsules met the responder criteria compared to 0 out of 13 patients in the placebo group. Statistical significance could not be achieved due to the low number of patients in each group and lack of primary response in placebo.

The effect of DS107 capsules was consistently higher than placebo for all of the efficacy endpoints evaluated in this study, both investigator scores and patient scores. Pruritus is the most important symptom for patients suffering from AD. It has a significant impact on sleep and quality of life (Hong *et al.* 2011). Pruritus sensation was significantly decreased from Baseline at Week 4 in patients receiving DS107 compared to patients receiving placebo. This difference in pruritus was both statistically and clinically significant as shown by a decrease in pruritus of 39.5% for patients randomized to DS107 and of only 10.05% in patients randomized to placebo at Week 4.

No deaths or SAEs were observed throughout the course of this study. There were no drug related AEs associated with safety lab results, physical exams or vital signs. AEs were mild to moderate and transient. The most common AEs observed in the DS107 group were gastrointestinal in nature. Overall the tolerance of DS107 capsules administered over 8 weeks was acceptable in comparison with placebo and DS107 appears safe and well tolerated.

